1. INTRODUCTION

This Drug Treatment and Handling Procedures (DTHP) describes the procedures used by the local Pharmacy and study clinic personnel in handling the study drug involved in this trial at both VA sites and non-VA sites. Drug accountability forms are used to maintain a record of all study drug received, dispensed, and returned by the participating medical center. A complete and accurate accounting for all investigational drugs is the responsibility of both the participating investigator and Pharmacy. Drug records are maintained by Pharmacy to meet the accountability requirements of the FDA (Food and Drug Administration), VA CSP (Department of Veterans Affairs Cooperative Studies Program), NHLBI (National Heart, Lung and Blood Institute), and the pharmaceutical industry.

2. **RESPONSIBILITIES OF PHARMACY**

Pharmacy is responsible for:

- a. Providing secure storage for the study drug in the pharmacy or elsewhere in the medical center.
- b. Maintaining complete and accurate records of all study drug received, dispensed and returned to CSPCRPCC (Cooperative Studies Program Clinical Research Pharmacy Coordinating Center).
- c. Verifying that informed consent has been obtained from each patient before any study drug is dispensed.
- d. Dispensing the study drug only upon the written order (e.g., outpatient prescription blank or inpatient doctor's order form) of a physician authorized to prescribe the study drug.
- e. VA SITES ONLY Providing the nursing unit with a copy of the Investigational Drug Information Record (VA Form 10-9012) for inclusion in the medical record of each patient randomized.

To coordinate pharmacy activities, CSPCRPCC recommends that a liaison pharmacist be designated for this study. The liaison pharmacist should: 1) meet with participating study clinic personnel before the study begins and 2) consult with the Clinical Research Pharmacist at CSPCRPCC when necessary. The Study Personnel Directory (DHP-1) lists the names, addresses and telephone numbers of other key personnel involved in the study. The liaison pharmacist should keep this list updated and retain copies of all correspondence received from CSPCRPCC regarding CSP #395.

3. RESPONSIBILITIES OF THE PARTICIPATING INVESTIGATOR

The participating investigator is responsible for providing their local Pharmacy with:

- a. A copy of the signed informed consent form for each patient to whom the study drug will be dispensed and administered.
- b. Prescriptions or inpatient doctor's order forms signed by the investigator or one of the other authorized physicians.
- c. The names of physicians currently authorized to prescribe the study drug at the participating medical center.

4. AUTHORIZED INVESTIGATORS

4.01 Participating Investigator

The study drug may be dispensed and administered only to patients who are under the supervision of the participating investigator and only for the purposes of this study. The participating investigator (henceforth referred to as the "Investigator") is the primary physician authorized by the FDA, VA CSP, NHLBI, and the local VA Research and Development Committee or Institutional Review Board to prescribe the study drug at the medical center. The investigator's name will appear on Form FDA 1572, "Statement of Investigator" [and on the Investigational Drug Information Record (Form DHP-2, VA Form 10-9012, Item 2 - VA SITES ONLY)].

4.02 Other Authorized Physicians

To authorize other physicians to prescribe the study drug, the investigator must include their names on Form FDA 1572, "Statement of Investigator" [and on the Investigational Drug Information Record (Item 19) - VA SITES ONLY]. CSPCRPCC will send the appropriate form(s) to the investigator prior to activating the study.

4.03 Authorizing New Physicians Throughout the Study

Additional physicians may be authorized to prescribe the study drug at any time by either completing an Addendum to FDA Form 1572 (Form DHP-3) or by submitting a memorandum to Pharmacy with the name(s) of additional physicians.

Blank Addendum to FDA Form 1572 forms will be available in Vol. II of the Operations Manual and from CSPCRPCC. The investigator (or his designee) should send the original of this form to CSPCRPCC, route the YELLOW copy to Pharmacy and retain the PINK copy for his files.

If the memorandum method is used, investigators (or his designee) should send the original to Pharmacy, a copy to CSPCRPCC and retain a copy for their files.

5. DESCRIPTION OF TREATMENT GROUPS

5.01 Outline of Study Design

The primary objective of this prospective, randomized, double-blind study is to evaluate the effect of β -adrenergic blockade on all cause mortality in patients with moderate to severe chronic heart failure in spite of conventional medical therapy. The basic study design is outlined in Figure 1.

[FIGURE 1]

```
Patient Eligible and Consenting? \rightarrow No \rightarrow EXCLUDE

\downarrow

Yes

\downarrow

RANDOMIZE

\downarrow

Bucindolol HCI

Placebo
```

Patients screened by study personnel and found to be eligible for participation in the study will be stratified according to (1) the hospital site and (2) the presence or absence of coronary artery disease. Patients will be treated and followed serially until death, refusal to continue study follow-up or termination of the study. Approximately 2,800 patients will enter the study during the three year enrollment period. The study will have a total duration of 4.5 years.

5.02 Treatment Groups

Patients will be assigned to one of two possible treatment groups:

- a. Bucindolol HCI (Code Named: B-395)
- b. Placebo

6. DESCRIPTION OF DRUG TREATMENT PHASES

6.01 Start-Up Treatment Phase

The start-up treatment phase begins the day the patient is randomized (Visit 2) and will end the day of Visit 10 (6-month visit). This phase consists of two parts: Part I (Titration) - a three month period during which B-395 is titrated to a target dose of either 50 mg BID for patients weighing \leq 75 Kg (165 lb), if tolerated or 100 mg BID for patients weighing > 75 Kg (165 lb), if tolerated; and Part II (Transition) - a three month period during which the highest possible dose without side effects is administered until the day of Visit 10 (6-month visit).

6.01 (a) Part I - Titration Period

The titration period begins the day the patient is randomized (Visit 2) and ends the day of Visit 9 (3-month visit). All study drug needed during the titration period can be obtained from the patient's B-395 Titration Kit.

During the titration period, the study drug will be increased at weekly intervals according to the following schedule:

TITRATION

Visit 1 (Week 00*):Initial screening - NO DRUG THERAPY

Visit 2 (Week 01): Randomization - Begin 3.0 mg BID x 7 days

Visit 3 (Week 02): Begin 6.25 mg BID x 7 days

Visit 4 (Week 03): Begin 12.5 mg BID x 7 days

Visit 5 (Week 04): Begin 25 mg BID x 7 days

Visit 6 (Week 05): Begin 50 mg BID x 7 days (target dose if patient weighs \leq 75 kg)

Visit 7 (Week 06): Begin 75 mg BID x 7 days (50 mg BID x 7 days if patient tolerates dose and weighs \leq 75 Kg)

Visit 8 (Week 07): Begin 100 mg BID x 7 days (target dose if patient weighs > 75 Kg) (50 mg BID x 7 days if patient tolerates dose and weighs \leq 75 Kg)

Week 08: Continue follow-up at target dose, if tolerated**

Week 09: Continue follow-up at target dose, if tolerated**

Week 10: Continue follow-up at target dose, if tolerated**

Week 11: Continue follow-up at target dose, if tolerated**

Week 12: Continue follow-up at target dose, if tolerated**

- (* Refers to week in titration period, e.g., Week 03 means third week of titration period)
- (** Beginning with Week 08 and continuing to the day of Visit 9 (3-month follow-up visit), the dose of B-395 administered should continue to be the highest possible tolerated dose without side effects.)

During the titration period, any one of the following dosing regimens can be prescribed:

DD Q BN BG TREATMEN SPER FMUTTED

Dose 3 mg BID	Dispense Capsules From: B-395 3 mg bottle (1) ¹	SIG Take 1 capsule BID
6.25 mg BID	B-395 6.25 mg bottle (1)	Take 1 capsule BID
12.5 mg BID	B-395 12.5 mg bottle (1)	Take 1 capsule BID
25 mg BID	B-395 25 mg bottle (1)	Take 1 capsule BID
37.5 mg BID	B-395 25 mg bottle	Take 1 capsule TID ²
50 mg BID	B-395 50 mg bottle (1)	Take 1 capsule BID
75 mg BID	B-395 50 mg bottle	Take 1 capsule TID ³
100 mg BID	B-395 100 mg bottle (1)	Take 1 capsule BID

¹ Number in parentheses refers to number of bottles in Titration Kit.

- ² For a 37.5 mg BID "interim" dose, change prescription directions to read "Take one capsule (25 mg) TID. This dosing regimen will be allowed only during the titration period.
- ³ For a 75 mg BID "interim" dose, change prescription directions to read "Take one capsule (50 mg) TID. This dosing regimen will be allowed only during the titration period.

(Note: Each B-395 dosage form will have a matching placebo.)

Should decompensation or adverse effects occur during the titration period, the investigator is encouraged to increase the patient's dose of diuretic and continue the study drug if at all possible. However, if the patient has an increase in heart failure symptoms, the investigator may slow drug titration by any of the following methods:

- a. choosing to delay the increase in the dose of study drug for 1-2 weeks,
- b. choosing not to further titrate the dose of study drug, or
- c. choosing to reduce the dose of study drug (i.e., go back to the previous dose) temporarily and defer further titration for at least 1-3 weeks.

Should other side effects of B-395 occur (e.g., impotence, dizziness, lightheadedness, nightmares, etc.), the dose of study drug may be decreased. Investigators are encouraged, however, to titrate patients to the full target dose (i.e., 50 mg BID for patients weighing \leq 75 Kg or 100 mg BID

for patients weighing > 75 Kg), if at all possible.

6.01 (b) Part II - Transition Period

Part II of the start-up treatment phase, the transition period, begins the day of Visit 9 (3month visit) and ends the day of Visit 10 (6-month visit). Prior to each patient's Visit 9 (preferably) or the day of Visit 9, study personnel must contact CSPCRPCC for a "Transition" bottle assignment.

Each "Transition" bottle contains a 3-month (98 days) supply of study drug. A number of these bottles, not predesignated for any particular patient, will be available at each participating medical center. The bottles will be individually numbered. SINCE THESE BOTTLES MAY CONTAIN EITHER ACTIVE OR PLACEBO STUDY DRUG, STUDY CLINIC PERSONNEL MUST CALL CSPCRPCC [[name] (VA SITES ONLY) OR [contact], [name]] FOR ALL "TRANSITION" BOTTLE ASSIGNMENTS.

Depending on the patient's highest tolerated dose during the titration period, study personnel should request one of the following types of "Transition" bottles indicated below:

TRANSITION BOTTLES

If the patient's highest tolerated dose during the titration period was:1	Request a Transition bottle containing:
3 mg BID	B-395 3 mg capsules
6.25 mg BID	B-395 6.25 mg capsules
12.5 mg BID	B-395 12.5 mg capsules
25 mg BID	B-395 25 mg capsules
50 mg BID	B-395 50 mg capsules
100 mg BID	B-395 100 mg capsules

(¹ NOTE: THESE ARE THE ONLY DOSING REGIMENS ALLOWED DURING THE TRANSITION PERIOD. If the patient's highest tolerated dose during the titration period was 37.5 mg BID, the dose will have to be either decreased to 25 mg BID or increased to 50 mg BID. If the highest tolerated dose during the titration period was 75 mg BID, the dose will have to be either decreased to 50 mg BID. BID or increased to 50 mg BID.

6.02 Maintenance Treatment Phase

Beginning the day of Visit 10 (6-month visit), patients will enter a maintenance treatment period for the duration of the study. During this period, patients return to the study clinic for Visit 10 (6-

month visit), Visit 11 (12-month visit) and then subsequent follow-up visits every six-months thereafter. [NOTE: It can be anticipated that some patients will need to return to the study clinic more frequently (e.g., every 4-8 weeks) due to the severity of their illness.]

At Visit 10 (6 month visit) and all subsequent follow-up visits thereafter, the study drug should be prescribed at the highest tolerated dose without side effects. For example, if the highest tolerated dose administered to a patient during Part II of the start-up phase was 25 mg BID, then the dose prescribed at Visit 10 should be 25 mg BID; if the highest tolerated dose administered to a patient weighing > 75 Kg during Part II of the start-up phase was 100 mg BID, then the dose prescribed at Visit 10 should be 100 mg BID. *(NOTE: A dose as low as 3 mg BID will be allowed.)*

During the maintenance treatment phase, if intolerable side effects occur with B-395 (any dose), the dose of study drug may be reduced temporarily or permanently, if necessary (see Section 10, Discontinuation of Study Drug for Clinical Reasons). The patient may at some later time tolerate re-titration to a higher dose.

7. DESCRIPTION OF STUDY DRUG

7.01 Study Drug

Patients randomized to treatment receive the study drug, either Bucindolol HCl or a placebo. Bucindolol HCl is a non-selective, beta-adrenergic blocking agent. It is currently an investigational drug. The study drug and matching placebo are made by Bristol Myers Squibb and donated by Cardiovascular Pharmacology and Engineering Consultants, Inc. (CPEC). The Albuquerque CSPCRPCC will distribute the study drug to each participating medical center for the duration of the study. Patients will be treated with the study drug for three years, on average.

7.02 Patient Kit Designs

7.02(a) B-395 Titration Kits

These are the only kits that CSPCRPCC will ship to each participating medical center prior to activating the study. All Titration Kit assignments will be made by the Palo Alto Cooperative Studies Program Coordinating Center (CSPCC). *(NOTE: Titration Kits may or may not be assigned in numerical order.)* Titration Kits contain B-395, either active or placebo. Each kit has six bottles of study drug. The study drug will be available in six clearly marked dosage forms: 3 mg, 6.25 mg, 12.5 mg, 25 mg, 50 mg, and 100 mg capsules.

Each Titration Kit contains a three month (98 days) supply of study drug and the bottles within each kit will contain varying quantities of drug:

	Drug	# Bts/Kit	Dosage Form	# Caps/bt
B-395	3 mg	1	3 mg capsules	196s
B-395	6.25 mg	1	6.25 mg capsules	182s
B-395	12.5 mg	1	12.5 mg capsules	168s
B-395	25 mg	1	25 mg capsules	210s
B-395	50 mg	1	50 mg capsules	189s
B-395	100 mg	1	100 mg capsules	126s

Each Titration Kit is identified with a specific kit number. Upon randomization, the Palo Alto CSPCC will assign each patient his own Titration Kit.

7.02(b) B-395 Maintenance Kits

Each B-395 Maintenance Kit will be identified with the same number as on the patient's Titration Kit. [NOTE: Drug assignment (active or placebo) also will be the same as in the patient's *Titration Kit.*] Each kit contains a 12-month supply of medication and each bottle has enough medication to treat the patient for three months (98 days). Subsequent Maintenance Kits will be prepared by CSPCRPCC and automatically shipped to each participating medical center.

POSSIBLE CONTENTS OF B-395 MAINTENANCE KITS

CODE NAME	STUDY DRUG	QUANTITY
B-395 3 mg	Bucindolol HCl or placebo OR	4 bottles (196)*
B-395 6.25 mg	Bucindolol HCl or placebo OR	4 bottles (196)
B-395 12.5 mg	Bucindolol HCl or placebo OR	4 bottles (196)
B-395 25 mg	Bucindolol HCl or placebo	4 bottles (196)
B-395 50 mg	Bucindolol HCl or placebo	4 bottles (196)

4 bottles (196)

(* number in parenthesis is the number of capsules in each bottle)

7.03 Transition Bottles

Also available at each participating center are unassigned bottles of B-395, called "Transition Bottles." Each of these bottles contains a 3-month (98 days) supply of the study drug. Both active and placebo Transition Bottles are available.

POSSIBLE TRANSITION BOTTLE ASSIGNMENTS

CODE NAME

STUDY DRUG

DAYS SUPPLY

B-395 3 mg	Bucindolol HCl or placebo	98 (196)*
B-395 6.25 mg	Bucindolol HCI or placebo	98 (196)
B-395 12.5 mg	Bucindolol HCI or placebo	98 (196)
B-395 25 mg	Bucindolol HCI or placebo	98 (196)
B-395 50 mg	Bucindolol HCI or placebo	98 (196)
B-395 100 mg	Bucindolol HCl or placebo	98 (196)

(* number in parenthesis is the number of capsules in each bottle)

One of these bottles will be dispensed to each patient at Visit 9 (3-month visit). These bottles can also be used for any dosing regimen changes that occur during the transition period or maintenance phase. One or more of these bottles can be obtained by calling the Albuquerque CSPCRPCC [VA SITES ONLY: FTS [contact]; ALL OTHERS: [contact], [name]]. (NOTE: Either the pharmacist or one of the study personnel must call the Albuquerque CSPCRPCC for all Transition Bottle assignments.)

Also available at each participating center are unassigned bottles of B-395, called "X-Bottles." Each bottle contains a two week (14 days) supply of the study drug. Both active and placebo X-Bottles will be available.

POSSIBLE X-BOTTLE ASSIGNMENTS

CODE NAME	STUDY DRUG	DAYS SUPPLY
B-395 3 mg	Bucindolol HCI or placebo	14 (28)*
B-395 6.25 mg	Bucindolol HCI or placebo	14 (28)
B-395 12.5 mg	Bucindolol HCI or placebo	14 (28)*
B-395 25 mg	Bucindolol HCI or placebo	14 (28)
B-395 50 mg	Bucindolol HCI or placebo	14 (28)
B-395 100 mg	Bucindolol HCl or placebo	14 (28)
-		

(* number in parenthesis is the number of capsules in each bottle)

If the patient is ever hospitalized without his bottle of study drug, one or more X-Bottles can be obtained by calling the Albuquerque CSPCRPCC [VA SITES ONLY: FTS [contact]; ALL OTHERS: [contact], [name]]. (NOTE: Either the pharmacist or one of the study personnel must call the Albuquerque CSPCRPCC for all X-Bottle assignments.)

7.05 De-Titration Cards

Three types of unassigned blistercards containing B-395, called "De-Titration Cards," are available at each participating medical center. Both active and placebo De-Titration Cards will be available.

POSSIBLE DE-TITRATION CARD ASSIGNMENTS

CODE NAME STUDY

DRUG DAYS SUPPLY

B-395 Card ABucindolol HCl or placebo9 days (18)*B-395 Card BBucindolol HCl or placebo6 days (12)B-395 Card CBucindolol HCl or placebo3 days (6)

(* number in parenthesis is the number of capsules on the card)

Whenever patients are on a daily dose of either **200 mg/day**, **150 mg/day (during titration period only)**, **100 mg/day**, or **50 mg/day** and need to have their study drug discontinued (temporarily or permanently), a De-Titration Card must be obtained by calling the Albuquerque CSPCRPCC [VA SITES ONLY: FTS [contact]; ALL OTHERS: [contact], [name]). (*NOTE: Either the pharmacist or one of the study personnel must call the Albuquerque CSPCRPCC* for all De-Titration Card assignments.) See Section 9.03 for prescribing de-titration doses.

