b) If a patient is not in incipient cardiogenic shock but has frequent recurrent fluid retention unresponsive to diuretic dosage increase or an increase in ACE inhibitor therapy, an investigator may choose to give intermittent low dose inotropic therapy. In this situation, it is preferable to administer a short 12-24 hour course of intravenous inotropic (preferably milrinone because its mechanism of action is not dependent on the beta-receptor) or vasodilator (nitroprusside, nitroglycerin) therapy during concomitant study drug therapy to reach compensation rather than discontinue drug altogether. Despite these efforts, should the patient not be able to be maintained on study drug therapy, the study drug dosage may be slowly, gradually reduced or discontinued. As acute withdrawal of beta-adrenergic blockade has been associated with cardiovascular events, it is recommended that drug dosage be slowly, gradually reduced rather than stopped acutely. **Should a patient not tolerate** study medication and the investigator wish to discontinue it, the Study Co-Chairman must be called prior to study drug reduction and the case discussed. When the patient is again compensated, the investigator and patient may choose to reinstitute the study medication and are encouraged to do so if at all possible. Re-titration starting at 3 mg orally twice daily should be performed as previously described, with weekly or biweekly up-titration.

c) In the face of incipient cardiogenic shock (fluid retention, hypotension, end organ hypoperfusion), the study drug should be immediately discontinued to administer inotropic therapy. When the patient is again compensated, the investigator and patient may choose to reinstitute the study medication. Re-titration starting at 3 mg orally twice daily should be performed as previously described, with weekly or biweekly up-titration.

4. **Reinstitution of study medication**

Reinstitution of study medication for patients who are again well compensated should be performed carefully using the following suggested guidelines:

a) For patients who have been off study medication less than 72 hours and who have not been in incipient cardiogenic shock, restart the study medication at the dose he/she was taking just prior to discontinuation.

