b) For patients who have been off study medication greater than 72 hours but less than 7 days and who have not been in incipient cardiogenic shock, restart the study medication at half the dose he/she was taking just prior to discontinuation.

c) For patients who have been off study medication greater than or equal to 7 days or have recently been in incipient cardiogenic shock, restart the study medication at 3 mg orally twice daily.

Other causes for discontinuation of study medication may include: a) intolerable side effects unresponsive to reduction in study drug dosage, b) performance of a cardiac or non-cardiac surgical procedure, or c) other acute medical illness which require cessation of drug therapy. For emergency surgery, study drug may be discontinued for 72 hours. For elective surgery where the patient will be unable to take medications for a prolonged period of time, slow, gradual reduction of the study drug dosage (cutting the dosage in half every 3 days) is recommended. In all cases, every effort should be made by the investigator to maintain or reinstitute the study drug.

5. Breaking the study medication code

The investigator should manage the patient by assuming he/she is on an active drug. In extraordinary, life-threatening circumstances, there may be a necessity to break the study code. In such circumstances, the investigator should attempt to reach a Study Co-Chairman, the Clinical Research Pharmacist or Biostatistician for instructions prior to breaking the code. In all other circumstances, temporary discontinuation of study medication should be handled without breaking the code, as described in Section D.1. on pages 28-29.

VIII. Statistical Analyses

A. Monitoring Reports

The Coordinating Center will be responsible for preparing reports to monitor the progress of the study for the Steering Committee and the Data and Safety Monitoring Board. Each type of report will include information on different aspects of the trial.

1. Executive Committee

The recruitment progress of each center and of the whole trial will be updated weekly for the Executive Committee.

2. Steering Committee Reports

To assess the progress of the daily operation of the study, the Coordinating Center will prepare routine reports for the Steering Committee. These reports will focus on the general status of **a**) patient recruitment, **b**) patient adherence, **c**) "effective adherent patient years,"

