9.03 Prescribing De-Titration Doses

Acute withdrawal of beta-adrenergic blockade has been associated with cardiovascular events.

Therefore, it is recommended that all doses of the study drug that are 25 mg BID or higher be detitrated over several days rather than stopped abruptly. The following de-titration schedules are recommended:

DRUG	IF PATIENT'S DOSE IS:	USE FOLLOWING DE-TITRATION SCHEDULE:
B-395	100 mg BID	Prescribe a B-395 Type A De-Titration Card. This card reduces the patient's dose as follows: 50 mg BID x 3 days, then 25 mg BID x 3 days, then 12.5 mg BID x 3 days, then discontinue.
B-395	75 mg BID Prescribe a B-395 1	Type A De-Titration Card. This card reduces the patient's dose as follows: 50 mg BID x 3 days, then 25 mg BID x 3 days, then 12.5 mg BID x 3 days, then discontinue.
B-395	50 mg BID Prescribe a B-395 1 then discontinue.	Type B De-Titration Card. This card reduces the patient's dose as follows: 25 mg BID x 3 days, then 12.5 mg BID x 3 days,
B-395	25 mg BID Prescribe a B-395 1	Type C De-Titration Card. This card reduces the patient's dose as follows: 12.5 mg BID for 3 days, then discontinue.
B-395	12.5 mg BID	No further de-titration is necessary.
B-395	6.5 mg BIDNo further de-titration	on is necessary.
B-395	3.0 mg BIDNo further de-titratio	on is necessary.

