10. DISCONTINUATION OF STUDY DRUG FOR CLINICAL REASONS

If a patient develops progressive worsening of his heart failure that does not respond to oral or intravenous diuretics and/or a reduction in the dose of study drug, the study drug may be discontinued. [NOTE: It is recommended that B-395 be de-titrated (see Section 9.03, Prescribing Detitration Doses) rather than abruptly withdrawn.] It is preferable to administer a 24-48 hour course of inotropic therapy (e.g., amrinone, dopamine or dobutamine) during concomitant beta-blocker therapy to reach compensation rather than discontinue the study drug altogether. Despite these efforts, if the patient is not able to be maintained on beta-blocker therapy, the study drug may be de-titrated or discontinued (depending on the dose).

If a patient does not tolerate the study drug and the investigator wishes to withdraw the patient, the Study Chairman or a physician member of the Steering Committee must be contacted prior to withdrawal and the case discussed.

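### Appendix B 7.05 requires a De-Titration Card at every discontinuation from the listed doses, which does not fit the recommended taper elsewhere or the body's immediate stop in shock and 72-hour stop for emergency surgery

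*Protocol*

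**What the plan says.** Appendix B, Section 7.05 describes the De-Titration Cards. For a patient on 200, 150 (titration period only), 100 or 50 mg/day, whenever the patient is on that dose "and need to have their study drug discontinued (temporarily or permanently), a De-Titration Card must be obtained" by calling the pharmacy coordinating center. The reader is then sent to Section 9.03 for prescribing.

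The rest of Appendix B is softer. Section 9.03 recommends that "all doses of the study drug that are 25 mg BID or higher be detitrated over several days rather than stopped abruptly". Section 10 says: "It is recommended that B-395 be de-titrated (see Section 9.03, Prescribing Detitration Doses) rather than abruptly withdrawn". Neither mentions incipient cardiogenic shock or emergency surgery.

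The body, VII.D.3 and VII.D.4, separates the situations:

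- Intolerance without shock, VII.D.3(b): "it is recommended that drug dosage be slowly, gradually reduced rather than stopped acutely".
- Shock, VII.D.3(c): "In the face of incipient cardiogenic shock (fluid retention, hypotension, end organ hypoperfusion), the study drug should be immediately discontinued to administer inotropic therapy".
- Emergency surgery, VII.D.4: "For emergency surgery, study drug may be discontinued for 72 hours".
- Elective surgery with a long period off oral medication, VII.D.4: "slow, gradual reduction of the study drug dosage (cutting the dosage in half every 3 days) is recommended".

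**The concern.** Section 7.05 is tied to every discontinuation, temporary or permanent, from four named doses. Two of these, 100 and 200 mg/day, are the target doses. The body sets out one situation in which the drug is to be stopped at once and another in which a short stop is permitted with no taper mentioned. A patient at a target dose who goes into incipient cardiogenic shock falls under 7.05 as written and also under VII.D.3(c), and no sentence in the protocol ranks the two.

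The protocol itself treats the choice as a safety matter. Both VII.D.3(b) and Section 9.03 warn that acute withdrawal of beta-blockade has been linked to cardiovascular events, yet the body still directs an immediate stop in shock. A site that followed 7.05 to the letter would act against the body in the situation where the body is most explicit.

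**Working it through.** The plan gives no figure to reproduce. The check compares the sections and converts the card contents into days.

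**Strength of the instruction, by section**

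| Section | Situation | Instruction |
|---|---|---|
| App. B 7.05 | Any discontinuation at 200, 150, 100 or 50 mg/day | Card must be obtained |
| App. B 9.03 | Stopping from 25 mg BID or higher | Taper recommended |
| App. B 10 | Worsening heart failure not responding to treatment | Taper recommended |
| Body VII.D.3(b) | Intolerance without shock | Taper recommended |
| Body VII.D.3(c) | Incipient cardiogenic shock | Immediate stop, no dose limit |
| Body VII.D.4 | Emergency surgery | 72-hour stop permitted, no taper mentioned |
| Body VII.D.4 | Elective surgery, prolonged time off medication | Taper recommended |

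There are therefore two mismatches: within Appendix B (must against recommended), and between 7.05 and the body (a card at every discontinuation against an immediate or 72-hour stop).

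**Length of each card**

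Inputs: capsules per card from 7.05 and step schedules from 9.03. Dosing is twice daily, so days = capsules / 2.

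- Card A (for 100 or 75 mg BID): 18 / 2 = 9 days. Schedule: 50, 25 and 12.5 mg BID, 3 + 3 + 3 = 9 days.
- Card B (for 50 mg BID): 12 / 2 = 6 days. Schedule: 25 and 12.5 mg BID, 3 + 3 = 6 days.
- Card C (for 25 mg BID): 6 / 2 = 3 days. Schedule: 12.5 mg BID, 3 days.

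The two sections agree on card length.

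**Against the body**

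- Shock: an immediate stop leaves 0 further days of drug. Completing a card leaves 9, 6 or 3, so none is compatible.
- Emergency surgery: 72 hours is 72 / 24 = 3 days. Cards A and B (9 and 6 days) exceed it. Card C (3 days) takes up the whole interval.

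**Dose coverage**

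Sections 6.01 and 9.05 allow an interim 37.5 mg BID during titration, which is 2 x 37.5 = 75 mg/day. It is above 25 mg BID, so the 9.03 recommendation covers it. Section 7.05 does not list it, and the 9.03 table has no schedule for it. The other interim dose, 75 mg BID (150 mg/day), appears in both.

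**The case against.** The strongest reply is that 7.05 belongs to a chapter describing supplies, and that its verb is *obtained by calling*, not *used*. The cards are unassigned and may be active or placebo, so each needs a central assignment. On that view the sentence fixes only how a card is requested. Prescribing is left to 9.03, which is advisory, and Section 10 ends by allowing either de-titration or discontinuation, depending on the dose. Pharmacy dispenses only on an authorized physician's written order (Sections 2 and 9.04), so no card reaches a patient in shock unless a physician prescribes it. Section 12.02 leaves patient-care decisions with the investigator. VII.D.2 points to the Operations Manual, which is not shown, for detailed guidance on gradual reduction.

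Much of this stands. A reader might infer that Appendix B makes a taper compulsory and so sets two opposite mandatory orders before the sickest patients. The text does not go that far: 7.05 speaks of obtaining a card, the prescribing sections recommend, the emergency-surgery sentence only permits, and nothing shows that emergency-surgery patients are the sickest.

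The reply does not remove the inconsistency. Section 7.03 and the X-Bottle text after it say that those supplies *can* be obtained by calling, and put the duty to call in a separate note. Section 7.05 carries the same kind of note but changes the main verb to *must* and ties it to every discontinuation. A site could reasonably read that as an obligation. Neither the physician's order nor the investigator's general responsibility tells the physician which section to follow.

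**Conclusion.** The inconsistency is real and unresolved in the protocol. Section 7.05 makes no exception, 9.03 and 10 only recommend, and the body directs an immediate stop in shock and permits a 72-hour stop for emergency surgery. The size is in days of further study drug: 9, 6 or 3 if a card is completed, against none under an immediate stop. The 75 mg/day gap is a smaller defect of the same kind.

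The conclusion assumes that 7.05 is read as requiring a card at each discontinuation. If it is read only as a telephone procedure, what remains is an ambiguous *must* that still needs clarifying.

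Two wider inferences are not supported. One is that every patient at 25 mg BID or above is affected: only those at a dose listed in 7.05 who stop because of shock or emergency surgery meet the conflict with the body, and the protocol gives no frequency for that. The other is that differing site practice distorts the primary endpoint. Treatment is double-blind, allocation is balanced within site, and the logrank analysis is by intention to treat and stratified by site. No effect on the mortality comparison is shown.

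**What to change.** Reconcile Appendix B 7.05, 9.03 and 10 with body VII.D.3 and VII.D.4:

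- State whether a De-Titration Card is mandatory or recommended, and use the same wording in all three appendix sections.
- State in 7.05 whether it applies where the body directs an immediate stop (incipient cardiogenic shock) or permits a 72-hour stop (emergency surgery).
- Cover the interim 75 mg/day dose in both 7.05 and 9.03.
- Add a cross-reference from Appendix B to VII.D.3 and VII.D.4.

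Which clinical rule stands is for the study's clinical leadership to decide. The cost is a wording change to Appendix B and a memo to sites and pharmacies. Sample size, data collection and analysis are unaffected.
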